4.1 Inclusion Criteria

To be included in the study, the following criteria must be met:

- A. 75 years of age or older
- B. Seated clinic systolic BP >150 mmHg in the untreated state
- C. At risk for cerebrovascular disease (history of smoking, dyslipidemia, type 2 diabetes, longstanding hypertension, family history). Patients must have visible (0.5% WMH or more) white-matter hyperintensity lesions on screening magnetic resonance imaging.
- D. To achieve success in maintaining a 24-hour systolic BP of <140 - 145 mmHg in the standard treatment group or a systolic BP <125 - 130 mmHg in the intensive treatment group, patients will be eligible for inclusion if (1) their clinic systolic BP is 150 - 170 mmHg, and they are taking 0 to 2 antihypertensives, (2) their systolic BP is > 170 mmHg and they are taking 0 to 1 antihypertensive.

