**Intensive Versus Standard Blood Pressure Lowering to Prevent
Functional Decline in Older People**

NCT01650402

Statistical Analysis Plan

IRB Approval Version 9/25/2018

INFINITY Statistical Analysis Plan (modification)

IRB Review
IRB NUMBER: IE-11-155S-2
IRB APPROVAL DATE: 09/25/2018

Principal Investigators: [name], [name]
Senior Statistician: [name]
Project Statistician: [name], MS
Date: 24 September 2018

Amendment 1.1

The primary objective of the INFINITY Trial is to assess causality between 24-hour systolic BP levels and preservation of mobility, cognitive and urinary function associated with reduced accrual of small vessel disease of the subcortical white matter in people over the age of 75 years.

A key hypothesis of the trial is that intensive treatment of 24-hour systolic BP to levels of 130 mmHg or less will result in improved gait time, stair descent time, and maximal gait velocity compared to treatment of 24 hour systolic BP to levels of 145 mmHg or less. This separation of ambulatory BP goals should achieve at least a ≥ 10 mmHg differences between groups over time. Previously, this difference has been shown to be responsible for the mobility decrements associated with WMH in older patients with systolic hypertension in a prospective cohort study (Circulation. 2011;124 (21):2312-9. doi: 10.1161/CIRCULATIONAHA.111.037036).

Prior to database lock of this trial in October 2018, we have added several secondary analyses to be pre-specified with their rationale as needed.

1. Change in white matter hyperintensity (%) (WMH) from baseline to 3 years
 - a. According to treatment group (primary analysis)

$$\begin{aligned} Y_{i1} &= \beta_0 + \beta_C x_i + \gamma_i + \varepsilon_{i1} \\ Y_{i2} &= \beta_0 + \beta_C x_i + \beta_L + \beta_T x_i + \gamma_i + \varepsilon_{i2} \end{aligned} \tag{1.1}$$

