Here, x_i is the treatment group indicator for participant i (one for intervention, zero for comparison); Y_{i1} is the SF-36 score for participant i at time 1 (baseline); Y_{i2} is the SF-36 score for participant i at time 2 (36 month follow-up); β_0 is interpreted as the average SF-36 score at baseline in the reference group; β_C is interpreted as the difference in the average SF-36 score at baseline between the intervention group and the reference group and will be zero if the two groups are exactly comparable in their baseline values; β_L is interpreted as the average change in SF-36 between 36 month follow up and baseline in the reference group; β_T is interpreted as the difference average change in SF-36 between 36 month follow up and baseline between the intervention group and the reference group and thus the parameter of primary interest; γ_i is a random intercept for participant i that addresses the correlation in SF-36 across the two time points; and ε_{i1} and ε_{i2} are the residual error terms at baseline and follow-up, respectively. Above analysis will be repeated for Sleep Scales (Pittsburgh Sleep Quality Index, and Epworth Sleep scale), and then as stratified analyses (b - e below) for both Sleep and SF-36 scales.

- b. Stratified according to < or > median age
- c. Stratified according to gender
- d. Stratified according to years of education
- e. Stratified according to a clinical diagnosis of minor or major depression
- f. Change from baseline in cognitive variables
- g. Changes from baseline in mobility parameters
- h. Changes from baseline in urinary function
- i. Change from baseline in WMH (%)

6. Regression of changes from baseline in WMH as a mediator of changes from baseline in mobility, cognition, urinary function and depressive symptoms. These analyses will be based on the analyses in (2) and (3), but with the addition of mediation by and interaction with WMH using the methods of Vanderweele (REF below).

$$Y_{i1} = \beta_0 + \beta_C x_i + \gamma_i + \varepsilon_{i1}$$

$$Y_{i2} = \beta_0 + \beta_C x_i + \beta_L + \beta_T x_i + \gamma_i + \theta_M (m_{i2} - m_{i1}) + \theta_{INT} x_i (m_{i2} - m_{i1}) + \varepsilon_{i2}$$

$$m_{i2} - m_{i1} = \alpha_0 + \alpha_1 x_i + \delta_i$$

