For mobility, cognition, and depression, variables are defined as in (1) with the following additions: δ_i is residual error in the model for change in WMH, and m_{i1} and m_{i2} are the values of WMH at baseline and follow-up, respectively. Some mediation measures of interest are as follows:

$$CDE = \beta_T$$

$$INT_{REF} = \theta_{INT} \alpha_0$$

$$INT_{MED} = \theta_{INT} \alpha_1$$

$$PIE = \theta_M \alpha_1$$

The controlled direct effect $CDE = \beta_T$ is the effect of treatment assignment in the absence of any WMH, $INT_{REF} = \theta_{INT} \alpha_0$ is the reference interaction between treatment assignment and WMH, $INT_{MED} = \theta_{INT} \alpha_1$ is the mediated interaction, and $PIE = \theta_M \alpha_1 x_i$ is the pure indirect effect. Combinations of these derived measures will be used to assess the degree of mediation, as described in VanderWeele. T.J. (2015). Explanation in Causal Inference: Methods for Mediation and Interaction, Oxford University Press. In particular, the proportion mediated is $\frac{INT_{REF} + INT_{MED} + PIE}{CDE + INT_{REF} + INT_{MED} + PIE}$.

Bootstrap standard errors and confidence intervals will be used for statistical inference, including estimation of standard errors and confidence intervals.

In secondary analyses, age, sex, and resultant ambulatory systolic BP at 36 months regardless of treatment assignment will be considered as mediators through similar methods. Specifically, age, sex, and systolic BP will replace $m_{i2} - m_{i1}$ in the model above and similar measures of interaction and mediation will be estimated.

7. Special Interest adverse events (falls, nervous system and vascular disorders) as related to numerous predictors of interest.

These outcomes are all count variables, so we use Poisson regression with each of the following predictors.

$$\log(\mu_i) = \log(n_i) + \beta_0 + \beta_1 x_i$$

Here μ_i is the count, n_i is the number of months in study, β_0 is the intercept with $\exp(\beta_0)$ interpreted as the rate of AE with mobility scale is zero, x_i is the predictor of interest, mobility scale and β_1 is the log rate ratio between groups and $\exp(\beta_1)$ is interpreted as the estimated ratio of rates for two subjects differing by one in their predictors of interest scale. This analysis will be repeated for the following predictors described below:

- a. Mobility variables
- b. Cognitive variables
- c. Treatment assignment
- d. Blood pressure
- e. Age
- f. Gender

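### SAP item 6 fixes the controlled direct effect at a mediator value of zero: a wrong label for WMH change, but a direct effect at 0 mmHg (or age 0) when systolic BP or age is substituted

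*SAP*

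**What the plan says.** SAP item 6 is headed as a "Regression of changes from baseline in WMH as a mediator of changes from baseline in mobility", with cognition, urinary function and depressive symptoms as further outcomes. The follow-up equation contains `beta_T*x + theta_M*(m_i2 - m_i1) + theta_INT*x*(m_i2 - m_i1)`. The mediator equation is `m_i2 - m_i1 = alpha_0 + alpha_1*x + delta`, where delta is the "residual error in the model for change in WMH". The mediator is therefore the change in WMH, not its level.

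Four components are defined: `CDE = beta_T`, `INT_REF = theta_INT*alpha_0`, `INT_MED = theta_INT*alpha_1` and `PIE = theta_M*alpha_1`. The SAP states that the CDE "is the effect of treatment assignment in the absence of any WMH". The proportion mediated is `(INT_REF + INT_MED + PIE)` divided by the sum of all four.

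For the secondary analyses, age, sex and "resultant ambulatory systolic BP at 36 months regardless of treatment assignment will be considered as mediators through similar methods". The mechanism is direct substitution: "Specifically, age, sex, and systolic BP will replace" the change term in the same model. No reference value or centring is given for any mediator.

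Protocol 4.1, criterion C, adds: "Patients must have visible (0.5% WMH or more) white-matter hyperintensity lesions on screening magnetic resonance imaging".

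**The concern.** A controlled direct effect is the treatment contrast with the mediator held at a named value. When treatment and mediator interact, it depends on that value. The SAP names none, and its formulas imply zero.

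For WMH change, zero has a clear meaning, but it is not the meaning the SAP gives. A report that followed the SAP's wording would misdescribe a correctly computed number.

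For systolic BP the variable substituted is a level. Zero then means a systolic BP of 0 mmHg, in a trial whose arm goals are 130 and 145 mmHg. The CDE and the reference interaction become long extrapolations with large, offsetting errors, and the proportion mediated inherits them. Age has the same problem, since everyone enrolled is 75 or older. Systolic BP is the quantity the trial manipulates, so a stated BP-mediated share would attract attention even as a secondary result.

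**Working it through.** **1. Reproduce the SAP's formulas.** From the follow-up equation, hold the mediator at `m*` and take the treatment contrast net of the baseline difference `beta_C`:

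- `CDE(m*) = beta_T + theta_INT*m*`
- `INT_REF(m*) = theta_INT*(alpha_0 - m*)`
- `INT_MED = theta_INT*alpha_1` and `PIE = theta_M*alpha_1`, neither containing `m*`

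Setting `m* = 0` returns the SAP's `CDE = beta_T` and "INT_{REF} = \theta_{INT} \alpha_0". No other value does so unless `theta_INT = 0`.

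**2. What does not depend on the reference value.** `CDE(m*) + INT_REF(m*) = beta_T + theta_INT*alpha_0`; `m*` cancels. The total effect, INT_MED and PIE are likewise free of it. The SAP's proportion mediated equals `1 - CDE/total`, so it does depend on `m*`.

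**3. WMH change.** `m* = 0` means `m_i2 = m_i1`, that is, no change from baseline to month 36. Absence of WMH would mean `m_i2 = 0`, and criterion C requires at least 0.5% in every participant at screening. The formula can stand; its description cannot.

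**4. Systolic BP: precision.**

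- From the documents: 70 per arm (Protocol 8.3, Sample Size and Randomization) and an intensive mean set at the 130 mmHg goal.
- Assumed: a standard mean of 142 mmHg (inside the 140 to 145 mmHg range that Protocol 5.1 gives as the purpose of down-titration), within-arm SD 8 to 15 mmHg, and residual gait SD 0.2 m/s.
- Simplification: a single follow-up regression with separate slopes by arm, instead of the SAP's two-time-point mixed model.

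`SE[CDE(m*)] = 0.2*sqrt(2/70 + ((130 - m*)^2 + (142 - m*)^2)/(69*SD^2))`

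For SD 10 at 0 mmHg: `0.2*sqrt(0.0286 + 37064/6900) = 0.465`. At 142 mmHg: `0.2*sqrt(0.0286 + 144/6900) = 0.044`.

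| Within-arm SD (mmHg) | SE at 0 mmHg (m/s) | SE at 142 mmHg (m/s) | Ratio |
|---|---|---|---|
| 8 | 0.580 | 0.049 | 11.7 |
| 10 | 0.465 | 0.044 | 10.4 |
| 12 | 0.388 | 0.042 | 9.3 |
| 15 | 0.311 | 0.039 | 8.0 |

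Simulation under the same assumptions agrees (SD 10: 0.471 against 0.045). The residual SD cancels from the ratio. At SD 10 the 95% half-width at 0 mmHg is about `1.96*0.465 = 0.91` m/s, against the 0.15 m/s seen in the prior cohort (Protocol 8.3).

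**5. Systolic BP: the share.** For illustration take a total effect of 0.15 m/s and a PIE of 0.05 m/s. These borrow the fall from 0.15 to 0.10 m/s that Protocol 8.2, Hypothesis 5, reports when WMH was added. With `alpha_0 = 142` and `alpha_1 = -12`, `beta_T = 0.15 - 0.05 - 130*theta_INT`.

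| theta_INT (m/s per mmHg) | CDE at 0 | Share at 0 | CDE at 142 | Share at 142 |
|---|---|---|---|---|
| -0.001 | 0.230 | -53% | 0.088 | 41% |
| 0 | 0.100 | 33% | 0.100 | 33% |
| +0.001 | -0.030 | 120% | 0.112 | 25% |

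For scale, the standard error of `theta_INT` at SD 10 is `0.2*sqrt(2/(69*100)) = 0.0034`. The interactions of plus or minus 0.001 in this table are under a third of one standard error. Sampling noise alone can therefore take the share at 0 mmHg below 0% or above 100%.

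**The case against.** Four arguments carry weight.

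- **The WMH point is only a label.** This stands. Item 6 defines the mediator explicitly as a change and elsewhere uses WMH as shorthand for it. A reader might infer that the trial would estimate a direct effect in people without WMH, whom it excludes. The equations do not support that: the computed quantity is the effect at zero change, and it stays the same once described correctly.
- **The SAP does not write out the BP formulas.** It speaks of similar methods and measures and refers to a textbook, so an analyst might recentre unprompted. This is possible, but no recentring is stated, and the sentence that says specifically what will be done describes plain substitution. The 0 mmHg reference is the literal result of the written rule.
- **The stakes are limited.** This also stands. BP as mediator is a secondary analysis. Protocol 8.2 already treats its own mediation results as preliminary for want of sample size, although there it describes a product-of-coefficients method. A reader might infer that all of the mediation results are compromised, but the quantities in step 2 of the working are not.
- **The size rests on assumptions.** The achieved means, SDs and interaction are not in the documents. If the true `theta_INT` is zero, the true CDE is the same at every reference value. The loss of precision remains, because the interaction is still estimated.

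The bootstrap intervals in item 6 would reveal the imprecision. They would not move the reference value into the data.

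**Conclusion.** The concern holds in two parts of unequal weight. For WMH change, the description of the CDE is wrong and nothing numerical follows. For systolic BP and age, the rule as written evaluates the CDE, the reference interaction and the proportion mediated at a value far outside the data. For BP the distance is 130 to 142 mmHg, or about 9 to 18 within-arm SDs over the assumed range of 15 to 8 mmHg.

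Under the stated assumptions the standard error of the CDE is about 8 to 12 times that at the standard-arm mean, and the share can fall outside 0 to 100% with a very small interaction. The direction of this result does not depend on the assumed SD or residual variance; its exact size does. The true values move only if `theta_INT` differs from zero. Sex coded 0/1 does not share the problem, since zero is then one of its two categories. The point merits correction because the written rule gives an uninterpretable result and is easy to repair.

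**What to change.** In SAP item 6:

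- Write `CDE(m*) = beta_T + theta_INT*m*` and `INT_REF = theta_INT*(alpha_0 - m*)`, and name `m*` for every mediator.
- For WMH change, state `m* = 0` and describe the CDE as the treatment effect if WMH did not change from baseline to month 36. Delete the reference to absence of WMH.
- For systolic BP and for age, pre-specify an in-range `m*` before database lock by centring the variable, for example at the standard-arm or the overall mean. Any in-range value is defensible. Say whether it is held fixed or recomputed across bootstrap samples.
- State the consequence of the choice. The standard-arm mean is `alpha_0`, so choosing it makes INT_REF zero by construction and reduces the share to `(PIE + INT_MED)/total`. The overall mean keeps all four components.

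The cost is a few lines of SAP text and one centred variable per secondary analysis in the code. No new data are needed. The SAP places the lock in October 2018; if it has passed, report the chosen reference value and label it as set after the plan.

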Product of coefficients methods^{35,36} will be used for formal statistical inference regarding the mediation. Specifically, we will estimate the product of the effect estimated for hypothesis 2 corresponding to Path A (the effect of intervention group on total WMH at T₃₆), and the effect estimated for hypothesis 3 corresponding to Path B (the effect of WMH at T₃₆ on gait velocity at T₃₆). The magnitude of this product turns out to be proportional to the change in the effect of intervention group on gait velocity at T₃₆ when WMH at T₃₆ is added to a regression model of gait velocity at T₃₆ as a function of intervention group. Similar models will be used to assess outcomes at T₁₈, and the cognitive outcomes. As formal tests for mediation using the product of coefficients method require larger sample sizes than available in this study, we will treat results from analyses in Hypothesis 5 as preliminary, to be potentially verified by a larger study should the main effects in Hypotheses 1-3 be confirmed.

Hypothesis 6: Diffusion tensor imaging (DTI) indices (FA, MD) at T₀ and at T₃₆ mediate the effect of treatment group, showing that the mechanism by which reduced ABP is linked to better mobility occurs by preserving brain WM microstructural integrity (FA, MD).

(Paths C – D&E) The same analysis as used for hypothesis 5, except that the mediating effect of the DTI indices will be assessed.

Missing Data.

Death and study attrition are associated with age-related diseases. Failure to account for this informative censoring may result in biased estimates of dementia risk and cognitive decline.³⁷ Hence, we will collect data by telephone to assess the degree to which living participants who fail to appear for their final assessment differ from participants who complete the study. As mentioned above, we will use telephone administration of a validated mobility assessment³⁹ and the method developed by [name] and colleague³⁰ to estimate mobility outcomes through multiple imputation or joint modeling that would have been

observed had the participants appeared for their clinical assessment. While our primary efficacy outcome analysis will be limited to participants who complete the study, this will be the first trial in aging with the potential to assess the impact of informative dropout beyond usual sensitivity analyses.

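### SAP item 6 omits the protocol's preliminary status for mediation and plans a proportion mediated that is uninterpretable when the total treatment effect is near zero

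*SAP*

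**What the plan says.** Protocol 8.2 (Hypotheses and Statistical Analyses), under Hypothesis 5, plans a product-of-coefficients analysis of WMH as mediator. It then limits its standing: "As formal tests for mediation using the product of coefficients method require larger sample sizes than available in this study", and so "we will treat results from analyses in Hypothesis 5 as preliminary, to be potentially verified by a larger study should the main effects" in Hypotheses 1 to 3 hold up. Hypothesis 6 applies the same analysis to the DTI indices.

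SAP item 6 has a wider scope: "Regression of changes from baseline in WMH as a mediator of changes from baseline in mobility, cognition, urinary function and depressive symptoms". It replaces the product of coefficients with a four-part decomposition (CDE, INT_REF, INT_MED, PIE) and states that "Combinations of these derived measures will be used to assess the degree of mediation". One summary is singled out, introduced by "In particular, the proportion mediated is": the sum of INT_REF, INT_MED and PIE, divided by that sum plus CDE. On inference it says "Bootstrap standard errors and confidence intervals will be used for statistical inference".

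Neither item 6 nor the rest of the SAP calls the mediation results preliminary. Nor does the SAP make the ratio depend on a treatment effect, or say what to report when the denominator is close to zero or the components differ in sign.

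**The concern.** The sample size that led the protocol to be cautious is unchanged in the SAP, but the caution does not appear there. The one summary the SAP writes out is a ratio to the total treatment effect. For any outcome that treatment does not move, that ratio divides by a quantity centred on zero.

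Mediation by WMH is the trial's mechanistic claim: Protocol 3 describes WMH accrual as the mechanism of functional decline, and Protocol 1.2 lists mediation among the objectives. A figure such as a 60% proportion mediated is easy to quote, and for an outcome with no treatment effect it would carry no information.

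**Working it through.** **1. The plan's own figure.** Protocol 8.3 (Sample Size and Randomization) gives 140 completers, 70 per arm, and 85% power for an R² increase of 0.0533 to 0.1800.
- f² = 0.0533/(1 − 0.1800) = 0.065, and λ = 140 × 0.065 = 9.1.
- With 3 covariates and an assumed two-sided 5% test, power is 0.850, so the stated figure reproduces.
- The powered effect in residual SD units is 2√0.0533/√0.82 = 0.51.
- The documents give no power or precision figure for mediation.

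**2. What the denominator is.** Take the SAP's outcome and mediator equations and subtract the expected change in the reference arm from that in the intensive arm. The result is β_T + θ_INT·α₀ + θ_INT·α₁ + θ_M·α₁ = CDE + INT_REF + INT_MED + PIE. The denominator is therefore the total treatment effect.

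**3. Closed form at zero total effect.** Write N for the numerator. The ratio N/(CDE + N) lies outside 0–1 exactly when N and CDE have opposite signs. Assume SD 1 for both changes, slope −0.3, no arm effect on WMH and no interaction. In units of 2/n:
- var(N) ≈ 0.09 + 0.91α₀²
- cov(N, CDE) ≈ −0.91α₀²
- var(CDE) ≈ 1 + var(N) − 0.18

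With r the correlation of N and CDE, P(outside 0–1) = ½ − arcsin(r)/π.
- α₀ = 0: r = 0, so P = 50%.
- α₀ = 1: r = −0.91/√(1 × 1.82) = −0.67, so P ≈ 74%.

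n cancels, so a larger trial would not help.

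**4. Simulation of the item 6 model on change scores.** 70 per arm, slope −0.3, α₀ from 0 to 1 SD, percentile bootstrap. A share of one third through WMH gives the widths in the non-zero rows.

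| True total effect | Ratios outside 0–1 | Median 95% interval width of the ratio |
|---|---|---|
| 0 | about 57–73% | about 7–22 |
| 0.25 SD (half the powered effect) | – | about 4–10 |
| 0.51 SD (powered effect) | – | about 1.0–1.5 |

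The interval for the absolute indirect effect is about 0.22–0.33 SD wide in every row. The lower simulated share (57%) sits above the closed form's 50%, so I read the result as roughly half to three quarters.

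**5. The same check in gait units.** From the protocol:
- gait SD = 0.15/(2√0.1082) = 0.228 m/sec
- detectable difference = 2√0.0533 × 0.228 = 0.105 m/sec
- slope = −0.063 m/sec per 1% WMH
- mediated share = (0.15 − 0.10)/0.15 = 1/3

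Assumed: baseline-to-36-month correlation 0.5, and reference-arm WMH change with mean 0.9% and SD 0.8%. The gate is a two-sided 5% test of the total effect.

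| Total effect (m/sec) | 95% range of ratio, no gate | Outside 0–1 | Gate passes | 95% range if gate passes |
|---|---|---|---|---|
| 0 | −13 to 16 | 76% | 5% | −0.80 to 1.01 |
| 0.05 | −4.3 to 6.0 | 55% | 26% | −0.58 to 1.03 |
| 0.105 | −0.37 to 1.58 | 23% | 77% | −0.27 to 0.94 |
| 0.15 | −0.09 to 0.96 | 8% | 97% | −0.09 to 0.89 |

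With correlation 0.8, 75% of ratios still fall outside 0–1 at zero effect. At 0.105 m/sec that falls to 6%.

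**6. INT_REF in the numerator.** INT_REF = θ_INT·α₀ does not involve α₁, the arm effect on WMH. Take α₁ = 0, so that nothing is mediated, with θ_INT = ±0.0315, α₀ = 0.9 and total effect 0.105. The ratio is then ±0.0315 × 0.9/0.105 = ±0.27.

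**The case against.** **The intervals give the warning.** This is the strongest reply, and it largely stands. With no total effect, 90–97% of the bootstrap intervals in the standardised simulation span both 0 and 1 (98% in the gait version). A careful reader would not be misled. What remains is the risk that the point ratio is quoted alone. The SAP does not name the type of bootstrap; the percentile method is my assumption.

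**The components are already planned.** The SAP defines all four and gives them bootstrap intervals, so the absolute indirect effect is available. That also stands: the fix changes emphasis and adds no analysis.

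Three stronger readings are tempting, and the documents do not support them.
- *The SAP removed a protocol gate.* In Protocol 8.2 the clause about confirmed main effects governs a later, larger verifying study. It does not govern whether mediation is computed in this trial. The SAP is also a modification that adds analyses, and nothing in it withdraws the protocol's text. The label is omitted, not revoked.
- *Mediation became a main analysis.* Item 6 calls the age, sex and blood-pressure versions secondary, which might suggest that the WMH version ranks higher. But the SAP's opening describes the added analyses as secondary, and Protocol 1.2 lists WMH mediation under secondary objectives.
- *The many outcomes produce a high rate of false mediation claims.* All WMH mediations share one arm-to-WMH regression, so false indirect effects tend to occur together. With no arm effect on WMH, simulation gives about an 8% chance of at least one. It reaches about 29% only if treatment moves WMH and WMH affects no outcome. The SAP also sets no 5% decision rule for item 6. The count of ratios is itself unclear, because no ratio is written out on the ordinal logit scale used for urinary severity and depression category.

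**Conclusion.** The concern holds in a limited form. SAP item 6 omits the protocol's preliminary status and plans, without any condition, a ratio that has no usable meaning for outcomes that treatment does not move. At zero total effect roughly half to three quarters of ratios fall outside 0–1, and the typical interval is 7 to 22 units wide on a scale meant to run from 0 to 1. Even at the powered effect the interval is about as wide as that scale.

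The exact widths rest on assumed inputs: the slope, the reference-arm mean WMH change, the mediated share and, for gait, the baseline-to-36-month correlation. The instability at zero effect does not depend on them. The absolute indirect effect is well behaved throughout. The primary efficacy analysis, gait velocity at 36 months, is unaffected. This is a worthwhile wording change, not a threat to the trial's main conclusion.

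**What to change.** In SAP item 6:
1. State that all mediation results are preliminary, for the reason given in Protocol 8.2.
2. Make the absolute indirect effect, INT_MED + PIE, with its bootstrap interval, the main mediation summary for every outcome. It is zero when treatment does not affect WMH.
3. Report a proportion mediated only where the total treatment effect has a 95% interval excluding zero. Take that effect from the item 2 model without mediator terms, because β_T in item 6 is the direct effect. Describe this as a new safeguard, not a restored rule.

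The gate has limits. In the gait check it cuts reported ratios at zero effect from all trials to about 5%, but those that pass remain imprecise. It also does not cure INT_REF in the numerator, so any ratio that is reported should show INT_REF separately beside it.

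The cost is SAP wording only, with no new data or models. The downside is that some outcomes will have no ratio. At a true effect of 0.05 m/sec the gate would pass in only about 26% of trials (correlation 0.5) to 55% (correlation 0.8).
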